### *3.6.2 Clinical Laboratory Tests*

Laboratory results and change from baseline will be summarized for each treatment group by visit using descriptive statistics. Summaries will be limited to values assessed by the Central Laboratory. Shift tables from baseline to subsequent study visits will also be generated. Counts and percentages of laboratory values outside the normal reference range will be summarized in the double-blind period and open-label period respectively.

Listings of laboratory values collected at local laboratories will be provided. Laboratory values outside the reference ranges will be flagged in the listings.

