### 3.1.3 *Definition of Baseline*

Baseline is defined as the last non-missing value prior to start of dosing with study medication (typically the Day 1 pre-dose value).

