### 3.3.7 Study Drug Exposure and Compliance

Duration of exposure to study drug will be calculated as (date of last dose – date of first dose + 1). If date of last dose is not available, the date of discontinuation from study will be used. Duration of exposure to study medication will be summarized with descriptive statistics for double-blind period, open-label period and both periods. Exposure data will be provided for the following intervals, defined to align with the efficacy endpoints:

- $\leq$ 4 weeks (days 1-29)
- $>$ 4 and  $\leq$ 12 weeks (days 30-85)
- $>$ 12 and  $\leq$ 24 weeks (day 86-169)
- $>$ 24 weeks (days  $>$ 169)

Percent compliance to study drug will be summarized for double-blind period, open-label period and both periods, calculated as follows:

$$\text{Percent Compliance} = 100 \times \text{number of capsules taken} / (6 \times \text{number of days in the specified period}).$$

Percent compliance to the study drug regimen will be summarized by treatment group based on the Safety Population using counts and percentages of subjects with compliance in the following categories:

- <80%
- 80-120%
- >120%

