### 3.6.1 Adverse Events (AEs)

An overview of AEs will be provided including counts and percentages of subjects (and event counts) with the following:

- Any TEAEs (overall and by maximum severity)
- Any study drug related TEAEs (overall and by maximum severity)
- Any treatment-emergent serious AEs (TESEAEs)
- Any TEAEs leading to discontinuation of study drug
- Any AEs leading to death

Counts and percentages of subjects (and event counts) will also be presented by system organ class (SOC) and preferred term (PT) using the Medical Dictionary for Regulatory Activities (MedDRA) Version 20.1 any TEAEs and TESEAEs for 3 Safety Populations separately. Counts and percentages of subjects (and event counts) will also be presented by PT in decreasing frequency for any TEAEs and TESEAEs for 3 Safety Populations (see 3.2.4 for definitions) separately.

TEAEs for the Safety Population in each period are defined as an event with a start date on or after the first study drug treatment in each period and up to the final observation in each period. Treatment periods for analysis of adverse event are defined in Section 3.2.4. TEAEs for the All CCX140-B Treated Population are defined as an event with a start date on or after the first dose of CCX140-B up to the final observation.

Listings will be presented specifically for SAEs and TEAEs leading to discontinuation of study drug.

The severity of AEs was assessed by the investigator using the following protocol definitions:

- Mild (Grade 1): no limitation of usual activities
- Moderate (Grade 2): some limitation of usual activities
- Severe (Grade 3): inability to carry out usual activities
- Life-threatening (Grade 4): an immediate risk of death
- Death (Grade 5)

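### For placebo-arm subjects, open-label change and shift displays for safety data start at Day 1, so they mix 12 placebo weeks with CCX140-B; the out-of-range table counts values rather than subjects

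*SAP*

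**What the plan says.** SAP 3.1.3 gives one baseline: "Baseline is defined as the last non-missing value prior to start of dosing with study medication (typically the Day 1 pre-dose value". Study medication here includes placebo. SAP 3.6.2 applies it to laboratory data: "Laboratory results and change from baseline will be summarized for each treatment group by visit using descriptive statistics", and "Shift tables from baseline to subsequent study visits will also be generated". SAP 3.6.3 (vital signs) and 3.6.6 (ACTG-BPNST) also summarize change from baseline and name no other reference point.

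Elsewhere the SAP does move the starting point. SAP 3.6.1 counts adverse events from the first dose in each period, and adds: "TEAEs for the All CCX140-B Treated Population are defined as an event with a start date on or after the first dose of CCX140-B". SAP 3.4.1 repeats the UPCR model in the open-label period both as change from baseline and as change from Week 12. SAP 3.2.4 sends all safety data to the safety populations, and 3.6 uses the treatment actually received, but neither section redefines baseline.

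For abnormal results, SAP 3.6.2 says: "Counts and percentages of laboratory values outside the normal reference range will be summarized in the double-blind period and open-label period respectively". By contrast, SAP 3.6.1 counts adverse events by subject, with event counts in addition.

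For exposure, SAP 3.3.7 begins "Duration of exposure to study drug will be calculated as", followed by last dose date minus first dose date plus one, and then says: "Duration of exposure to study medication will be summarized with descriptive statistics for double-blind period, open-label period and both periods".

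**The concern.** Placebo subjects who enter the extension cross from no drug to CCX140-B at Week 12, at an open-label dose currently planned as 15 mg twice daily. They are the only subjects in the trial with their own 12-week untreated run-in before active dosing. A change measured from Day 1 does not isolate what happened after the switch.

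The data involved matter. Protocol 2.4 regards the red-cell findings in animals as likely to carry over to humans, and describes the dog neuropathy as incompletely reversible and of unknown mechanism. Hematology and the ACTG-BPNST are the instruments that watch for these effects. As written, no planned laboratory, vital-sign or ACTG-BPNST table shows the off-drug to on-drug change within subjects.

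The counting unit is a separate weakness in the same section. With arms of 10, a percentage of values says little about how many people are affected.

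**Working it through.** **Plan's own figure.** Blinded dosing is 84 days and open-label dosing 84 days (SAP 2.2.2). 84 + 84 = 168 days, and 168 / 7 = 24 weeks, which agrees with the total treatment period in the protocol synopsis.

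**Share of the change that is placebo time.** Inputs: target days from SAP 3.1.2; first CCX140-B dose in the placebo arm taken as Day 85 (assumption: on schedule, no gap). Span from Day 1 = target day − 1. Days since first CCX140-B = target day − 85. Placebo share = 84 / span.

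| Visit | Target day | Days from Day 1 | Days since first CCX140-B | Placebo share |
|---|---|---|---|---|
| Week 13 | 92 | 91 | 7 | 84/91 = 92% |
| Week 16 | 113 | 112 | 28 | 84/112 = 75% |
| Week 20 | 141 | 140 | 56 | 84/140 = 60% |
| Week 24 | 170 | 169 | 85 | 84/169 = 50% |

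**Can the printed tables be re-based?**

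- *Mean change:* yes, approximately. Subtract the Week 12 row from a later row. This is exact only if the same subjects contribute to both, and entry to the extension is conditional (Protocol 5.4).
- *Spread of change:* no. SD² of the Week 12 to Week 24 change = SD₁₂² + SD₂₄² − 2·r·SD₁₂·SD₂₄, and the within-subject correlation r does not appear in by-visit summaries.
- *Shift tables:* no. A placebo subject normal at Day 1, low by Week 12 and low thereafter shows a normal-to-low shift at every open-label visit, although nothing changed on drug. A subject low at Day 1, normal at Week 12 and low again on CCX140-B shows low-to-low, so a shift on drug is missed.

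**Values against subjects.** Illustration, assuming 10 subjects, the 4 open-label visits above, and values pooled over visits within the period: 10 × 4 = 40 values. Four abnormal values give 4/40 = 10%. If they all come from one subject, 1/10 = 10% of subjects is affected; if from four subjects, 4/10 = 40%.

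**Exposure.** A placebo-arm completer has 168 days of study drug over both periods (band above 12 to 24 weeks), but 84 days of CCX140-B (band above 4 to 12 weeks). A placebo subject who stops after 28 open-label days shows 84 + 28 = 112 days (band above 12 to 24 weeks) against 28 days of CCX140-B (band up to 4 weeks). Completers in the three active arms have 168 days on either count.

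**The case against.** The strongest reply is that little is hidden. Week 12 blood is drawn before dosing (Protocol 7.7), so the Week 12 row for the placebo arm is its last value before CCX140-B, printed in the same table as the later visits. The display is descriptive, with no model to bias. Change from Day 1 is a legitimate summary; UPCR keeps it and adds change from Week 12. This stands for means. It does not reach shift tables or the spread of individual change. What is missing is a supplementary display; the Day 1 baseline itself is not wrong.

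Several stronger readings are tempting, and the documents do not support them.

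- A reader might infer that CCX140-B exposure is misreported. SAP 3.3.7 also reports open-label exposure on its own, and for the placebo arm that line is its CCX140-B exposure. Only the both-periods total and the day bands combine the two, and these are labelled as study drug or study medication.
- A reader might infer that the out-of-range table also mixes placebo and active time. It is split by period, so its weakness is only the unit.
- A reader might infer that baseline abnormality is ignored throughout. Shift tables classify results by baseline status; the gap is in the out-of-range table taken alone.

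It is also fair to say that the SAP does not state whether values are pooled over visits, that its wording may be loose, and that a separate programming specification (SAP 7) may settle the layout. The contrast with the subject-level wording for adverse events still makes the unit worth stating.

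**Conclusion.** The point holds as a worthwhile, inexpensive improvement. For up to 10 placebo-arm subjects, the open-label changes in laboratory tests, vital signs and ACTG-BPNST, and the laboratory shifts, are measured across 12 placebo weeks: 92% of the span at Week 13, falling to about 50% at Week 24. By-visit means partly compensate; shift tables and within-subject spread do not. The shares assume the first CCX140-B dose on Day 85 and visits on target.

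A reader might infer that the safety comparison between arms is biased. It is not: the randomized comparison is the 12-week blinded period, where Day 1 is the right baseline in every arm. Nor can the effect be sized in laboratory units, because the documents give no figure for drift on placebo. The 5 mg and 10 mg arms may change dose at Week 12, so their later change from Day 1 spans two regimens, but their first CCX140-B dose is at Day 1 and the first-dose problem does not arise.

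The exposure element is minor and a matter of labelling. The counting-unit element stands on the SAP's wording; the 10% against 40% example shows the ambiguity under an assumed pooled layout and is not a predicted result.

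**What to change.** 1. **Baseline (SAP 3.1.3, 3.6.2, 3.6.3, 3.6.6).** Keep change from Day 1. For placebo-arm subjects, add a CCX140-B baseline, the last value before the first open-label dose. Use it for change in laboratory tests, vital signs and ACTG-BPNST, and for laboratory shift tables, in the open-label and All CCX140-B Treated displays. For subjects randomized to CCX140-B this baseline is the Day 1 value. The protocol times Week 12 blood before dosing; the SAP should say that Week 12 vital signs and ACTG-BPNST are treated in the same way.
2. **Out-of-range table (SAP 3.6.2).** Report, per period, the number and percentage of subjects with at least one out-of-range result that is new or worse than baseline, in place of value counts or beside them. State which baseline applies in the open-label period: the CCX140-B baseline for the placebo arm, Day 1 for the others.
3. **Exposure (SAP 3.3.7, minor).** Label the both-periods total and the day bands as study drug including placebo, or add CCX140-B exposure counted from the first CCX140-B dose (84 instead of 168 days for a placebo completer).

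Cost: SAP wording, one extra baseline flag in the analysis datasets, and a few more tables. The Week 12 assessments are already scheduled, so no new data are needed.

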### *3.6.3 Vital Signs*

Vital signs parameters will be summarized using descriptive statistics for each treatment group by visit. The change from baseline will also be summarized.

### *3.6.4 Electrocardiograms*

Abnormal ECG findings will be listed by treatment group and study visit, and clinical significance of abnormalities indicated.

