9.3.6. Safety Analyses

All clinical safety and tolerability data will be listed by treatment group and by subject, and will be summarized by treatment group and visit.

Treatment-emergent adverse events (TEAE) will be summarized for each treatment group by MedDRA System Organ Class (SOC) and preferred term (PT), by relatedness and maximum severity. Treatment-emergent serious adverse events (TESAE) and TEAE leading to study withdrawal will be separately listed and may be summarized if warranted by the subject incidences.

Vital signs and laboratory test results, and their changes from baseline will be summarized by treatment group and visit. Abnormal laboratory values will be flagged in the data listing. Shift tables will be generated by study visit.

Individual ECG findings and change from baseline in ECG findings will be listed by treatment group, subject, and study visit, and summarized by treatment group and visit.

Findings from physical examinations will be listed.

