#### *2.3.6.4 Electrocardiogram*

Safety endpoints include clinically significant abnormal electrocardiogram (ECG) findings. A 12-lead ECG, after resting for at least 3 minutes, will be performed at screening and assessed for any clinically significant abnormalities. All abnormalities will be recorded in the EDC system. Assuming the ECG abnormality does not preclude study entry, an ECG may be repeated as clinically indicated.

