## **6 CHANGES FROM PROTOCOL-SPECIFIED STATISTICAL ANALYSES**

Per ChemoCentryx's request, responder analysis and MCP-MOD have been added for the analysis of the primary efficacy endpoint.

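### SAP 3.6.4 replaces the protocol's ECG summary by arm and visit with a listing of abnormal ECGs, and SAP section 6 does not declare the change

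*SAP*

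**What the plan says.** **ECG, protocol.** Section 9.3.6 requires that individual findings and "change from baseline in ECG findings will be listed by treatment group, subject, and study visit, and summarized by treatment group and visit". The Synopsis and section 9.2.4 carry the same commitment. The endpoint named in 9.2.4 is clinically significant abnormal ECG findings.

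**ECG, SAP.** Section 2.3.6.4 keeps that endpoint: "Safety endpoints include clinically significant abnormal electrocardiogram (ECG) findings". The analysis in section 3.6.4 is one sentence: "Abnormal ECG findings will be listed by treatment group and study visit, and clinical significance of abnormalities indicated". It plans no counts, no percentages and no comparison with baseline.

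**Adverse events, protocol.** Section 9.3.6 says treatment-emergent adverse events (TEAEs) "will be summarized for each treatment group by MedDRA System Organ Class (SOC) and preferred term (PT), by relatedness and maximum severity".

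**Adverse events, SAP.** Section 3.6.1 keeps the tables by SOC and PT for TEAEs and treatment-emergent serious events, for each of three safety populations. It places relatedness and maximum severity in the opening overview only.

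**Precedence and changes.** Protocol section 9 and SAP section 1 both give the SAP priority over the protocol's analysis methods. SAP section 6 records only that "responder analysis and MCP-MOD have been added for the analysis of the primary efficacy endpoint".

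**The concern.** Safety and tolerability is a primary objective, and the only route from the collected ECGs to a reported result is SAP 3.6.4. A listing of abnormal tracings shows individual cases. It does not say what share of each arm was abnormal at a visit, how many subjects in that arm had an ECG at that visit, or whether an abnormality is new since baseline. The last of these matters because the protocol allows some ECG abnormalities at entry: exclusion 17 bars clinically significant ones, and section 8.2.1 foresees others that do not preclude entry.

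On adverse events, a reader will be able to see how many related or severe events each group had in total, and how many events of each type, but not how many events of a given type were severe or related. Protocol section 4 directs its special-interest monitoring at particular types of event (hemolysis, neuropathy, infection, liver injury), and a row of Protocol Table 2 is triggered by severity and relatedness together. The missing cross-classification is therefore one that the trial's own safety monitoring relies on.

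**Working it through.** Neither document gives a figure for this point, so the check is mainly a comparison of text.

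**Step 1: which text governs.** The SAP supersedes the protocol's methods, so where the two differ the SAP decides what is produced.

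**Step 2: the repeated safety assessments side by side.**

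| Assessment | Protocol 9.2.4 and 9.3.6 | SAP |
|---|---|---|
| Laboratory tests | Values and change, by arm and visit; shift tables | Kept (3.6.2) |
| Vital signs | Values and change, by arm and visit | Kept (3.6.3) |
| ACTG-BPNST neuropathy tool | Change from baseline in score | Kept, by arm and visit (3.6.6) |
| ECG | Findings and change: listed, and summarised by arm and visit | Abnormal findings listed only (3.6.4) |
| Physical examination | Listed | Listed (3.6.5) |

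Four assessments have a change-from-baseline plan in the protocol. Three keep it and ECG does not. Physical examination was specified as a listing in both documents, so nothing was lost there.

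**Step 3: what the missing table would hold.** The Time and Events Table schedules ECGs at screening, Day 1, Weeks 12, 13 and 24, and the follow-up visit. Week 12 is the one post-baseline visit at the end of blinded treatment, so it carries the randomised comparison with placebo. At Weeks 13 and 24 continuing subjects are on open-label drug, and a display by randomised arm is descriptive.

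**Step 4: how precise it would be.** The planned size is 10 per arm. If no subject in an arm has a clinically significant abnormal ECG, the one-sided 95% upper bound on the true rate is 1 − 0.05^(1/10) = 0.259. An empty cell is therefore compatible with a rate of up to about 26%. The table would be descriptive, but it states the numerator and denominator that such a bound needs.

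**Step 5: adverse events.** SAP 3.6.1 states: "Counts and percentages of subjects (and event counts) will also be presented by system organ class (SOC) and preferred term (PT"), covering TEAEs and treatment-emergent serious events, and adds PT tables in decreasing frequency. The overview counts all TEAEs and drug-related TEAEs, each by maximum severity. What the SAP does not specify is SOC/PT by relatedness or SOC/PT by maximum severity.

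**Step 6: declaration.** Protocol section 9 says departures from the protocol will be documented and described in the final report. SAP section 6 lists two additions, both for the primary efficacy endpoint. Neither safety reduction appears there.

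**The case against.** The best defence is that the SAP is entitled to supersede the protocol, that the loss is small, and that cardiac effects are not a focus of this trial. Protocol 2.4 reports no adverse findings in cardiovascular safety pharmacology or the hERG assay, the special-interest events do not include cardiac ones, and an independent committee reviewed unblinded safety data. With about 10 subjects per arm, anyone can count from a listing, and SAP section 7 promises listings of all available data. These points stand as reasons not to inflate the issue. They do not explain why a retained endpoint has no planned tabulation, or why section 6 is silent. On adverse events, the protocol sentence could be read loosely as asking for separate summaries, which the overview would partly meet; that is one reason this part is minor.

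A reader might infer more than the documents support:

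- **That the SOC/PT breakdown is gone.** SAP 3.6.1 keeps it; only the cross-classification is missing.
- **That there will be no between-arm ECG information at all.** Abnormal ECGs are still listed by treatment group and visit, and ECG abnormalities reported as adverse events enter the SOC/PT tables. What is missing is a planned tabulated summary.
- **That a measurable QTcF comparison is being discarded.** With an assumed SD of change of 15 to 20 msec, the 90% half-width for a dose against placebo would be 1.734 × SD × √(2/10), or 11.6 to 15.5 msec. But the SD is not in the documents, and they do not show that interval values are captured after baseline: section 8.2.1 says only that abnormalities are recorded. The 450 msec value is an example in a screening exclusion, not an on-study flag. These figures therefore do not measure the loss.
- **That the top dose had never been given.** Protocol 6.4 describes earlier once-daily dosing and projects twice-daily exposure. It says that 30 mg as a single dose had not been given; it does not say so of 15 mg twice daily.
- **That the summary was removed on purpose.** Nothing in the documents shows intent.

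**Conclusion.** The plan is wrong as written: SAP 3.6.4 is an undeclared departure from the protocol's safety analysis. Followed literally, it produces no tabulated comparison of arms for a safety endpoint that the SAP itself retains. The size is one of four change-from-baseline safety analyses lost, in an area the protocol does not single out for special monitoring, with 10 subjects per arm planned. No numerical effect on the trial's conclusions can be derived from the documents. The missing SOC/PT tables by relatedness and by maximum severity are a minor second point of the same kind.

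The conclusion rests on the texts as they stand. It assumes that the separate programming specifications, which are not among the documents, do not already restore these tables. If they do, the SAP still needs to say so.

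**What to change.** In SAP 3.6.4, add by treatment group and visit: the number of subjects with an ECG; counts and percentages with an abnormal and with a clinically significant abnormal finding; and the shift from baseline in these categories, using the last pre-dose value as defined in SAP 3.1.3. Add descriptive statistics for ECG intervals and their change only if interval values are in the database. If they are not, say so.

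In SAP 3.6.1, add SOC/PT tables by relatedness and by maximum severity for the three safety populations.

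Declare and justify in SAP section 6 any part that is not restored.

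The cost is a few standard tables. The counts need no new data, provided the database records whether each scheduled ECG was done; abnormalities are already to be recorded under Protocol 8.2.1.

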### *3.6.5 Physical Examinations*

Physical examination findings will be listed by treatment group and study visit, and clinical significance of abnormalities indicated.

